NOTE: The requirement for maintaining a current disclosure form on file with the University's Conflict of Interest Office extends primarily to Yale University and Yale-New Haven Hospital personnel. **Whether or not they are required to maintain a disclosure form with the University's Conflict of Interest Office, all investigators and individuals deemed otherwise responsible by the PI who are listed on the protocol are required to disclose to the PI any interests that are specific to this protocol.**

SECTION II: GENERAL INFORMATION

1. **Probable Duration of Project:** State the expected duration of the project, including all follow-up and data analysis activities.

The duration of the pilot in its entirety will be 1 year; March 2018-March 2019

2. **Targeted Enrollment:** Give the number of subjects: 40

a. targeted for enrollment at Yale for this protocol 40 If this is a multi-site study, give the total number of subjects targeted across all sites N/A

b expected to sign the consent form 60

c. expected to complete some or all interventions for this protocol? 40

SECTION III: FUNDING, RESEARCH TEAM AND TRAINING

1. **Funding Source:** In IRES
2. **Research Team:** In IRES

SECTION V: RESEARCH PLAN

1. **Statement of Purpose:** State the scientific aim(s) of the study, or the hypotheses to be tested.

HIC# 2000022733

We will conduct a pilot study evaluating the feasibility and acceptability of providing a computer-based program (CBT4CBT), used for the treatment of substance use disorders, in a church setting. Forty Black adults with a current DSM-5 alcohol or substance use disorder will utilize the ‘CBT for CBT’ program over a period of 8 weeks. Primary outcomes will be acceptability and feasibility of providing the treatment in a church setting. If found to be acceptable and feasible, with preliminary promise for reductions in substance use, the next step would be to adapt the computer intervention for this population and conduct a randomized controlled trial.

Specific aims are as follows:

- (1) To determine the feasibility of recruiting Black adults with substance use disorders (BSUD) from within the Black church and immediate surrounding community and retaining BSUD in treatment, within a church setting.
- (2) To evaluate the acceptability of CBT4CBT with BSUD in a church setting and to identify if religious behaviors led by trained church based health advisors (CHA), may increase the likely suitability of this intervention within the Black church.

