3. **Research Plan:** Summarize the study design and research procedures using non-technical language that can be readily understood by someone outside the discipline. Be sure to distinguish between standard of care vs. research procedures when applicable, and include any flowcharts of visits specifying their individual times and lengths.

B. METHODOLOGY

B.1.a. Recruitment of BSUD:

Forty Black adults, 20 male and 20 female participants, who self-identify as Black and want help with drug and/or alcohol problems in the church setting, will be recruited from within the church itself, Dixwell Avenue Congregational UCC and the two predominately Black neighborhoods in New Haven, CT, Dixwell and Newhallville, immediately surrounding the church. Given past successes with the needs assessment study, using targeted recruitment strategies, including culturally normative flyers disseminated by Black church clergy, online and print ads in Black church bulletins, and culturally sensitive ads on urban radio stations, these same tools will be utilized to recruit the research participants for the pilot project. Participants will be screened by research staff using the DSM-5 Substance Use Criterion to ensure all potential participants meet criteria for a SUD as defined by DSM 5. Inclusion criteria: (1) at least 18 years of age (2) has at least one SUD diagnosis as defined by the DSM 5 (3) self-identified with having a SUD and confirmed after DSM 5 criterion checklist; Exclusion criteria: (1) inability to provide informed

HIC# 2000022733

consent or participate in the study procedures as proposed in the consent (2) active suicidal or homicidal ideation and (3) current engagement in substance abuse treatment.

B.1.b. Recruitment of Church Based Health Advisors (CHAs):

Community partner, [name]--pastor of Dixwell Avenue Congregational United Church of Christ, will advertise the role of the CHA (CHA description in attached documents) in the church bulletin, through church meetings, and by peer nomination, in order to identify church leaders interested in this role. All CHAs must be a member of a Black church in the targeted Newhallville/Dixwell neighborhoods, be at least 18 yo, and have the ability to read and write. It would be preferable, but not necessary, if a CHA had lived experience with drug and/or alcohol use. 12 CHAs will be recruited in total, 10 consistent leaders, and 2 alternates for emergency/unplanned absences.

B.2. Procedure:

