A total of 5 cohorts, each with 8 participants, will meet at Dixwell church on pre-determined days to take the intervention (CBT4CBT) online, simultaneously. Participants in each cohort will complete each online module at their own speed, but meet together on a weekly basis for a total of 8 sessions (8 weeks). Tablets, Wi-Fi hot spots and internet service, will be purchased for the church and made available to participants during the 8 weekly sessions, in addition to allocated times, for review of immediate session topics after each week of a CBT module.

The ten church staff members, known as CHAs, will undergo the informed consent process to participate in the research program, along with two extensive, 8-hour training days, including, but not limited to, topics such as the modules of CBT4CBT, basic research principles, and foundational knowledge related to addiction and drug and alcohol treatment. The CHAs, will then meet together to identify religious practices that can be coupled with each CBT4CBT module, to reinforce lessons taught in each respective module. Two CHAs will be assigned to each cohort, and will meet the 8 participants on a weekly basis, with a back-up CHA also assigned, for emergency/unplanned absences, to ensure each cohort has at least 2 CHA present. All religious practices will be led by the CHA, with any spiritual insights from participants reframed by the CHA, to reinforce lessons from a CBT4CBT module.

A member of the research team will also be present during all CBT4CBT sessions to collaborate with research participants and CHAs. **Table 1**, included below provides a detailed outline of the CBT4CBT modules and approximated spiritual practices to accompany each module. Final practices to accompany each CBT module will be pre-determined by the CHAs.

Table 1. CBT4CBT Intervention Topics

Every Session (led by CHA)	*Check-in, Opening Prayer, Scripture Reading, Praise & Worship (2 song selections) Testimony (optional), Ending Prayer *The proposed agenda above will be modified based on input from CHA.
Session 1	Recognize the Triggers -items that trigger substance use
Session 2	Coping with Craving -skills & tools to deal with cravings
Session 3	Plan Don't Panic -identifying problems in advance & coming up with solutions
Session 4	Go Against the Flow -learning how to make safer decisions
Session 5	Stand up for Yourself -learning how to be assertive & stand up for yourself
Session 6	Stop and Think -challenging negative thoughts

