Assessments include measures used to: 1) Describe the sample, 2) Measure primary and secondary outcomes during treatment. We will rely on widely used, well-validated instruments. Please see a complete list of the Assessment Battery Below in **Table 2**.

Table 2 Assessment Battery

Instrument name	Interview or self-report	Rater	Screen	Pre Tx	Weekly	Monthly	Post Tx (8 wks)
Informed Consent Quiz	Self-report	P	X				
*Baseline Demographics	Interview	RA	X				
Inclusion/Exclusion criteria	Interview	RA	X				
Follow-up contact & tracking sheet		RA	X				X
DSM-5 Criterion Checklist	Interview	RA	X				X
Urine toxicology screen, breathalyzer		RA	X	X	X		X
Timeline Follow-back/ Substance Use Calendar (SUC)	Interview	RA	X		X		X
Brief Symptom Inventory (BSI)	Interview	RA		X	X		X
Quality of Life Scale	Interview	RA		X			X
Treatment Utilization	Interview	RA		X		X	X
Evaluation of treatment, endpoint	Self-report	P					X
Daily Spiritual Scale	Self-report	P		X			X
Multi Group Ethnic Identity Measure	Self-report	P		X			X
Racial Pride Scale	Self-report	P		X			X
Recovery Markers Questionnaire	Self-report	P		X			X
Religiosity Scale	Self-report	P		X			X
Religious Methods of Coping to Gain Control	Self-report	P		X			X
Sense of Community Index	Self-report	P		X			X
*Qualitative Exit Interview Guide	Interview	PI					X

*CHAs will complete Baseline Demographics and Qualitative Exit Interviews only

A pictorial overview of the pilot study is outlined below in **Figure 2**.

Figure 2: Overview of Pilot Study: 40 participants, divided into 5 cohorts of N=8, (1) Feasibility (2/3 Retention

HIC# 2000022733

N=27); (2) Acceptability (Evaluation of Treatment Survey, Qualitative Exit Interview); (3) Substance Use (Urine Tox, Breathalyzer); (4) Recovery Goals (Recovery Markers Questionnaire); (5) Functioning (Social Functioning Scale)

4. Genetic Testing N/A

5. Statistical Considerations: Describe the statistical analyses that support the study design.

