Data Analysis Plan for a pilot feasibility study of providing substance use treatment in the Black Church

PI: [name] [name]
Data Manager: [name]

Updated 12/3/2020

This study is being conducted to determine the feasibility of recruiting Black adults with substance use disorder from within the Black Church and immediate surrounding community and retaining them in treatment, within a church setting.

A consort diagram will be used to assess the flow of participants from screening through week 8. Since this is a single arm trial cross tabs and ANOVA's will be run to describe the sample on characteristics such as age, sex, education, marital status.

1. We will measure acceptability of treatment by giving each participant a post-intervention satisfaction survey as well as a qualitative exit interview, to fully assesses satisfaction with the intervention, perception of outcome, attitudes about spiritual practices accompanying CBT modules, and whether the participant would recommend this program to a friend.

This will be done by calculating the mean and standard deviation of each question.

2. Feasibility will be measured by at least 2/3 of participants (N=27) completing the CBT4CBT intervention.

This will be a done by calculating the mean and standard deviation of number of sessions attended over the 8-week trial.

3. Secondary analyses will include significant reductions in drug use, as measured by mean change scores in the severity and quantity of substance use, and functioning over the course of treatment intervention.

As the study was implemented this outcome was refined to better reflect the aims of the study (recruiting and retention participants in treatment). A change score will not be calculated.

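### SAP item 1 summarises each acceptability question only by a pooled mean and SD, which does not show what proportion of participants found the program or its spiritual practices unacceptable

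*SAP*

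**What the plan says.** Protocol Section V.1 makes acceptability and feasibility the primary outcomes. Aim 2 is to evaluate acceptability and "to identify if religious behaviors led by trained church based health advisors (CHA), may increase the likely suitability of this intervention". Protocol Section V.5 lists acceptability among the criteria for deciding whether to adapt the program further.

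SAP item 1 measures acceptability with a satisfaction survey and a qualitative exit interview. Together they cover satisfaction, perceived outcome, "attitudes about spiritual practices accompanying CBT modules", and whether the participant would recommend the program. The analysis is one sentence: "This will be done by calculating the mean and standard deviation of each question". No response-category count, interval, acceptability threshold or handling of missing surveys is given.

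The only breakdown in the SAP is that "cross tabs and ANOVA's will be run to describe the sample on characteristics such as age, sex, education, marital status". It describes the sample and is not linked to acceptability.

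Protocol Table 1 proposes a religious agenda for every session, including "Opening Prayer, Scripture Reading, Praise & Worship (2 song selections"), and says that it will be modified with input from the church-based health advisors (CHAs). Table 2 schedules the "Religiosity Scale", the Daily Spiritual Scale and a religious coping scale before and after treatment. Neither Section V.5 nor the SAP names an analysis that uses them.

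**The concern.** What a team needs from an acceptability item is how many participants found the program, or its religious part, acceptable and how many did not. A mean and SD do not answer that when responses are skewed or polarised, and polarisation is plausible for questions about prayer and worship. A favourable mean can sit alongside quite different numbers of unfavourable ratings.

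Protocol Section V.1 says the next step, if results are encouraging, is to adapt the program and run a randomized trial. Whether one in eight or nearly one in three participants disliked the spiritual practices bears on that adaptation. The survey responses contain the answer, but the planned summary discards it.

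The survey is also taken only after treatment. Anyone put off by the content may have left by then, so the number of surveys behind each mean matters as well.

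**Working it through.** **Figures in the plan.** No scale, SD, threshold or power is stated for acceptability, so there is no acceptability figure to reproduce. The nearest checkable figure is the feasibility count: 40 × 2/3 = 26.67, rounded up to 27, which agrees with the SAP. I use 40 (target enrolment) and 27 (the completion threshold) as a plausible range for the number of surveys. The 27 is an assumption, because the protocol intends to re-interview everyone.

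**Does a mean and SD fix the number dissatisfied?** Assume a 1-5 item with 40 responses. Take 26 fives, 2 fours and 12 twos.
- Sum = 130 + 8 + 24 = 162, so mean = 162/40 = 4.05.
- Sum of squares = 650 + 32 + 48 = 730, so SD = √[(730 − 162²/40)/39] = √(73.9/39) = 1.38.
- Ratings of 1 or 2: 12/40 = 30%, exact (Clopper-Pearson) 95% CI 17% to 47%.

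Now take 23 fives, 6 fours, 6 threes and 5 ones.
- Sum = 115 + 24 + 18 + 5 = 162.
- Sum of squares = 575 + 96 + 54 + 5 = 730. Mean and SD are therefore identical, 4.05 and 1.38.
- Ratings of 1 or 2: 5/40 = 12.5%, exact 95% CI 4% to 27%.

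Listing every 40-person pattern with this sum and sum of squares gives 17 patterns. The number rating 1 or 2 runs from 5 to 12. The number rating 4 or 5 runs from 26 (65%) to 34 (85%). The planned summary cannot distinguish between them.

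**Does it show who is dissatisfied?** No. Take 16 fives, 12 fours, 4 threes and 8 twos: mean 3.90, SD 1.15. Divide these 40 scores into groups of 28 and 12. The same scores can give group means of 4.57 and 2.33, or 3.93 and 3.83. The pooled result is the same either way.

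**How much could baseline religiosity add?** Using the Fisher z interval, tanh(atanh r ± 1.96/√(n − 3)), which is only approximate for a rank correlation:

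| Observed r | n = 40 | n = 27 |
|---|---|---|
| 0.3 | −0.01 to 0.56 | −0.09 to 0.61 |
| 0.5 | 0.22 to 0.70 | 0.15 to 0.74 |

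A median split is no more informative. The 95% half-width for a difference in means is t(38) × √(2/20) = 0.64 SD at 20 v 20, and t(25) × √(1/13 + 1/14) = 0.79 SD at 13 v 14. Only strong associations would be visible, so this part can be no more than exploratory.

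**The case against.** **The exit interview covers the same ground.** Spiritual practices are assigned jointly to the survey and the interview. The protocol schedules the interview after treatment, and Aim 3 is to obtain qualitative data. In a pilot of 40 it is a natural way to learn who disliked the religious content and why. This stands, and any quantitative result should be read with it. It does not supply the missing proportions, and neither document states how the interviews will be analysed.

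**The SD would warn the reader.** At a mean of 4.05 on a 1-5 item the largest possible SD is about 1.72, so 1.38 does signal a low tail. That is fair. But the enumeration shows that the SD leaves the size of the tail open between 5 and 12 people.

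**The example is chosen by hand and the scale is assumed.** True. It shows what the summary permits, not what will happen.

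**No threshold turns a mean into a decision.** Correct. Nothing in either document is triggered by a particular mean, which limits the consequence.

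**Not linking baseline scales to satisfaction is no error.** This also stands. Protocol Section V.3 (5) says some measures serve to describe the sample, and other scales in Table 2 likewise have no stated analysis. The link is optional.

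**A stronger reading a reader might infer** is that the pooled mean hides religious content that suits churchgoers but not non-church residents. Recruitment does extend beyond the congregation: participants "will be recruited from within the church itself, Dixwell Avenue Congregational UCC and the two predominately Black neighborhoods in New Haven, CT", and church membership is required of CHAs but not of participants. But the documents do not say that neighbourhood recruits are non-churchgoers. All participants want help in the church setting, much of the outreach runs through clergy and church bulletins, and Section V.2 (A.3) puts regular attendance at 65% to 80% of adults in urban Black communities. The session agenda is a proposal that the CHAs may change. Aim 2 asks whether the religious behaviors "may increase the likely suitability of this intervention within the Black church", not for which subgroup.

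**Conclusion.** The point holds as a limitation of the reporting method. The stated analysis of a primary outcome does not show what proportion of participants rated the program or its spiritual practices unfavourably. In the example the gap is a range of 12.5% to 30% unfavourable, with identical mean and SD. That range assumes a 1-5 item and 40 respondents; another scale or number would give other figures, but the principle does not depend on them.

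This is an inexpensive improvement to a descriptive plan, not a fault that invalidates it. The claim that a churchgoer versus non-church-resident difference is being concealed should not be made: no such groups are defined in the documents. A low score on a religiosity scale would not define them either, since a median split puts about half the sample in the low group even if nearly everyone attends church.

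**What to change.** In SAP item 1, keep the mean and SD and add for each question:
- the number and percentage in each response category;
- the favourable proportion with an exact 95% CI, with the favourable categories named before the data are summarised;
- the number of enrolled participants who did not complete the survey.

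Optionally, and labelled exploratory with no hypothesis test, report a rank correlation with 95% CI between the continuous pre-treatment Religiosity Scale and the spiritual-practice and recommend-to-a-friend items, read alongside the exit interviews. Do not use a median split, and do not present the result as a comparison of churchgoers with non-church residents.

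The cost is a few lines of SAP text and one extra table from data already scheduled for collection. The intervals will be wide at 27 to 40 respondents, and the added table cannot recover the views of people who left before the survey; it can only show how many surveys are missing.

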As this is a pilot evaluation of the acceptability and feasibility of providing CBT4CBT in a Black church setting, data analyses will focus on determining whether the results warrant further adaptation of the existing CBT4CBT program. Criteria for this will include (1) measuring acceptability of treatment by giving each participant a post-intervention satisfaction survey as well as a qualitative exit interview, to fully assesses satisfaction with the intervention, perception of outcome, attitudes about spiritual practices accompanying CBT modules, and whether the participant would recommend this program to a friend. (2) Feasibility will be measured by at least 2/3 of participants (N=27) completing the CBT4CBT intervention. Secondary analyses will include significant reductions in drug use, as measured by mean change scores in the severity and quantity of substance use, and functioning over the course of treatment intervention. The proposed sample size (n=40) is adequate to detect this effect.

SECTION VI: RESEARCH INVOLVING DRUGS, BIOLOGICS, PLACEBOS AND DEVICES

N/A

SECTION VII: HUMAN SUBJECTS

1. Subject Population: Provide a detailed description of the types of human subjects who will be recruited into this study.

Participants:

BSUD (20 male and 20 female) who self- identify as Black and want help with drug and/or alcohol problems in the church setting will be recruited from within the church itself, Dixwell Avenue Congregational UCC and the two predominately Black neighborhoods in New Haven, CT, Dixwell and Newhallville, immediately surrounding the church.

CHAs—12 Black church members and leaders who are well versed in the practices of the Black church will be recruited by [name] to serve in this role.

2. Subject classification: Check off all classifications of subjects that will be targeted for enrollment in the research project. Will subjects who may require additional safeguards or other considerations be enrolled in the study? If so, identify the population of subjects requiring special safeguards and provide a justification for their involvement.

- | | | |
|--|--|--|
|  Children |  Healthy |  Fetal material, placenta, or dead fetus |
|  Non-English Speaking |  Prisoners |  Economically disadvantaged persons |

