- c. Copy, paste, and then tailor an appropriate Data and Safety Monitoring Plan from <http://www.yale.edu/hrpp/forms-templates/biomedical.html> for
 - i. Minimal risk
 - ii. Greater than minimal/moderate risk
 - iii. High risk
- d. For multi-site studies for which the Yale PI serves as the lead investigator:
 - i. How will adverse events and unanticipated problems involving risks to subjects or others be reported, reviewed and managed?
 - ii. What provisions are in place for management of interim results?
 - iii. What will the multi-site process be for protocol modifications?

Overall level of risk for participants is minimal given the nature of this project and procedures in place for careful identification of potential subjects, informed consent process, and protection of confidentiality. We have used the CBT4CBT program successfully and safely in multiple previous trials {[name], 2008 #10267; [name], 2009 #10266; [name], 2014 #11309}.

A Data and Safety Monitoring Board (DSMB) will monitor this project because this population might be considered vulnerable due to their substance use. This board is already in place for the Yale Psychotherapy Development Center ([name], Faculty Advisor). The DSMB is composed of Yale investigators who are independent of the proposed trial and experienced in various aspects of the conduct of clinical trials for the treatment of addictive disorders. We have developed a standard DSMB report form that is used in all Center related trials that summarizes, *on a quarterly basis*:

1. Recruitment, retention, and follow-up rates for the study and compares them to target rates.
2. Rates of data completeness and availability of primary outcome data.
3. Occurrence of AEs and SAEs.
4. Report of study progress since the last report.
5. Rates of recruitment of women, minorities, and children with respect to targets.

These reports are generated by the Data Manager each quarter and signed by each study PI prior to their submission to the DSMB. DSMB comments are documented and forwarded to the Yale IRB at the time of the annual review and re-approval.

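### The feasibility rule is a count of completers (27 of 40), but the SAP's analysis is a mean and SD of sessions attended, which need not show whether 27 completed

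*SAP*

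**What the plan says.** Protocol Section V.1 states: "Primary outcomes will be acceptability and feasibility of providing the treatment in a church setting". Section V.5 sets the rule: "Feasibility will be measured by at least 2/3 of participants (N=27) completing the CBT4CBT intervention". The same section makes feasibility one of the criteria for deciding whether the program should be adapted further.

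SAP item 2 repeats the rule and then gives its method: "This will be a done by calculating the mean and standard deviation of number of sessions attended over the 8-week trial". Item 2 mentions no count, proportion or comparison with 27.

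Neither document defines completion, and the text supports two readings:

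- **Module completion.** Section V.5 and SAP item 2 speak of completing the intervention. Section XI.2 pays $50 for finishing every module.
- **Retention.** Aim 1 refers to "retaining BSUD in treatment, within a church setting" and the SAP introduction to "retaining them in treatment, within a church setting". The Figure 2 legend labels the same N=27 "1) Feasibility (2/3 Retention".

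Two other outputs touch on retention. The SAP says: "A consort diagram will be used to assess the flow of participants from screening through week 8". The quarterly DSMB report in Protocol Section IX.3 covers "Recruitment, retention, and follow-up rates for the study and compares them to target rates".

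**The concern.** The rule needs a number of people, and the method gives an average number of sessions. Many different completer counts can share one mean and SD, so the stated analysis may not answer the stated question.

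Attendance is also only a proxy on the module reading. Section V.3 B.2 describes 8 weekly sessions but 7 modules. Sessions 1 to 7 carry one topic each, participants work at their own pace, and Session 8 is a closing meal and graduation.

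The decision on further adaptation rests partly on this criterion, and it is the only primary outcome with a numerical threshold. If the analysis leaves it open, the team would have to choose a completion definition and a count later, possibly with the data in view.

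**Working it through.** **The plan's own figure.** Section II.2 targets 40 participants. 40 × 2/3 = 26.67, which rounds up to 27, and 27/40 = 67.5%. The stated N=27 is reproduced. The denominator is therefore the 40 in the intervention, not the 60 expected to sign consent, for whom 27/60 = 45%.

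**Do a mean and SD fix the count?** Take n = 40 and 0 to 8 sessions each. The sample SD is √[(Σx² − (Σx)²/n)/(n − 1)], so datasets with equal Σx and Σx² have the same mean and SD. Completion is undefined, so the cut-offs below are assumptions, as are the means and SDs.

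*Setting A: mean 6.0, SD 2.0.* Σx = 240 and Σx² = 39 × 4 + 240²/40 = 156 + 1440 = 1596.

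*Setting B: mean 6.5, SD 2.207.* Σx = 260 and Σx² = 1880; SD = √[(1880 − 1690)/39] = 2.207.

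An integer-programming search over all attendance distributions gave the fewest and most people who could reach each cut-off:

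| Setting | Cut-off (sessions) | Fewest | Most |
|---|---|---|---|
| A | at least 6 | 17 | 36 |
| A | at least 7 | 11 | 31 |
| B | all 8 | 11 | 27 |

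Every range contains results that meet 27 and results that miss it.

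**Pairs on either side of the threshold.** Counts are listed for 0, 1, …, 8 sessions. Both members of a pair have the same mean and SD.

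| Setting, cut-off | 26 reach it (missed) | 27 reach it (met) |
|---|---|---|
| A, at least 6 | 2,0,0,2,1,9,9,5,12 | 3,0,0,0,0,10,4,18,5 |
| A, at least 7 | 2,1,2,0,0,1,8,26,0 | 1,3,0,0,0,9,0,24,3 |
| B, all 8 | 0,0,1,8,1,3,0,1,26 | 0,0,0,8,5,0,0,0,27 |

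Check of the first pair:

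- Left: Σx = 6 + 4 + 45 + 54 + 35 + 96 = 240; Σx² = 18 + 16 + 225 + 324 + 245 + 768 = 1596.
- Right: Σx = 50 + 24 + 126 + 40 = 240; Σx² = 250 + 144 + 882 + 320 = 1596.

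**A wider gap.** Take completion as all 8 sessions. With 27 people at 8, 11 at 3 and 2 at 2, Σx = 253 and Σx² = 1835. With 8 people at 8, 27 at 7 and 5 at 0, both sums are the same. Each dataset has mean 6.325 and SD 2.454, but the first has 27 completers and the second 8.

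**The mean can rank results backwards.** On the same cut-off, 27 people at 8 and 13 at 0 meet the rule with a mean of 216/40 = 5.40. With 26 at 8 and 14 at 7 the rule is missed with a mean of (208 + 98)/40 = 7.65. Exactly 27 completers is compatible with means from 5.40 to 7.675, and exactly 26 with means from 5.20 to 7.65.

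**Precision at the threshold.** The exact (Clopper-Pearson) 95% interval for 27/40 is 51% to 81%.

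**The case against.** The strongest reply is that the count will be available anyway. The SAP introduction presents feasibility as recruitment and retention, and its CONSORT diagram runs to week 8. The 2/3 figure is the only numerical retention target in the documents, so it is the natural target for the DSMB comparison. A reader could probably set a week-8 count against 27. This has force on the retention reading, but the link is only implied. No text ties either output to the rule or says that reaching week 8 means completing the program, and it does not settle the module reading.

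Second, attendance is a reasonable proxy by design: modules are taken on tablets at the weekly sessions, one topic per session for the first seven. That is fair, and the documents do not show how far attendance and completion diverge. But even a perfect proxy would have to be counted against a cut-off, not averaged.

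Third, this is a single-arm pilot with no hypothesis test for feasibility, and the threshold is one of two criteria. True, but the point asks for no test or power calculation, only that the trial evaluate its own rule.

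Finally, the examples show what is possible, not what is likely. Setting B reaches 27 only at its extreme. Setting A makes the point alone.

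**Conclusion.** The concern holds. SAP item 2 states a completer-count rule for a primary outcome and attaches an analysis that need not decide it. On neither reading of completion is the mean and SD of sessions the number that the rule requires. The mismatch should be corrected before the feasibility result is reported.

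The claim is that the summary need not determine the count, not that it never can: a mean of 8 with an SD of 0 would settle it. The numerical ranges rest on assumed cut-offs and assumed means and SDs with n = 40. They concern attendance only and say nothing about the size of any error in module completion.

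**What to change.** Replace the analysis sentence in SAP item 2 with wording such as:

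> Feasibility is the number and proportion of completers among all eligible participants enrolled into the intervention (planned 40). Participants withdrawn or lost before completing count as non-completers. The criterion is met if the proportion is at least 2/3 (27 if 40 enrol; the proportion governs if the number differs).

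Then:

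- **Define completion**, reconciling the module wording in Section V.5 and SAP item 2 with the retention label in Figure 2. One example is all 7 modules according to the program log.
- **Label the definition post hoc** if it was set after data were seen. The SAP is dated 12/3/2020 and the protocol planned to end in March 2019; the documents do not say whether data had been examined.
- **Keep the mean and SD of sessions** as a descriptive supplement, and show the completer count in the CONSORT diagram.
- **Optionally**, add an exact 95% confidence interval.

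The cost is low: a few sentences and one count. Section V.3 B.2 says the program database tracks modules accessed and progress for each participant, and the Section XI.2 payment already requires someone to establish who finished every module. The source of that completion status should be named. The downsides are that the result may look less favourable than a mean and that the definition may have to carry a post hoc label.
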